5.7.1.2. Graphical Presentation

The following plots of individual data will be made:

- The time of collection of the pre-dose sample will be set to zero;
- Actual sampling time will be used for individual graphs as horizontal axes;
- Individual plasma concentration vs. time curves on Day -3 of PK-Lead-in and Day 15 of Cycle 1 will be generated by each dose level on linear scales;
- Individual plasma concentration vs. time curves on Day 1 of Cycle 2 onward will be generated by each dose level on linear scales.

The following plots of summarized data will be made;

- The time of collection of the pre-dose sample will be set to zero;
- Nominal sampling time will be used for mean graphs as horizontal axes.
- Mean plasma concentration (Mean \pm SD) vs. time curves on Day -3 of PK-Lead-in and Day 15 of Cycle 1 will be generated on linear and log-linear scales combining the curves for all dose levels in one plot;
- Mean plasma concentration (Mean \pm SD) vs. time curves on Day 1 of Cycle 2 onward will be generated by each dose level on linear scales;
- The data will be handled for the graphical presentation in the same fashion as for the summary of individual plasma concentrations.

5.7.2. Plasma PK Parameters

5.7.2.1. PK Parameter Calculation

For the Dose Escalation part (Part A1) of the study, PK parameters will be calculated by standard noncompartmental analysis (NCA) on Day -3 of PK Lead-in (for QD dosing) or Day 1 (for BID dosing, if applicable) and Day 15 (for both QD and BID dosing, if applicable) of Cycle 1.

The calculation of PK parameters in plasma will be based on the actual time after the dosing. The time of collection of the pre-dose sample will be set to zero for calculating PK parameters. The plasma concentration data for the calculation of PK parameters will be handled as described in Section 5.7.1.1 except that plasma concentrations below the LLOQ appearing in terminal time-points will be treated as missing.

Plasma PK parameters will be estimated as follows:

- C_{\max} (Maximum observed concentration);
- T_{\max} (Time of maximum observed concentration);

C_{\max} and T_{\max} are obtained from experimental observations. If C_{\max} occurs at 2 or more time points, T_{\max} is assigned to the time of the earliest occurrence. In determining T_{\max} , the actual time of the plasma sample relative to the dosing time will be used.

- AUC_{last} (Area under the curve from the time of dosing to the time of last quantifiable concentration);
- AUC_n (Area under the curve from the time of dosing to time n);

AUCs will be calculated using the linear log trapezoidal rule. AUC_n will be calculated by the program as a partial area depending on the dosing interval. Prior to calculating AUCs and $T_{1/2}$ (terminal elimination half-lives), the individual plasma concentrations by time profiles are evaluated on an individual basis as to their suitability for inclusion in these calculations. In calculating AUCs, plasma concentrations that are listed as BQL are treated as missing, except for the following cases: for single-dose profiles, BQL concentrations prior to the first quantifiable concentration will be set to 0; for multiple-dose profiles, BQL concentrations at the beginning of the profile may be set to 0 or C_{\min} . The pre-dose sampling time will be set to 0. For single-dose profiles, the concentration at pre-dose will be set to 0.

- $T_{1/2}$ (Terminal half-life)
 $T_{1/2}$ is calculated from the terminal log-linear phase of the concentration-time curve which is identified by least-squares linear regression of at least three data points, which yield a minimum mean square error. Visual inspection and improvement in the adjusted square of the coefficient of correlation (RSQ) will be used to determine those time points prior up to but not including C_{\max} . Points included in the estimation of terminal elimination rate constant will be flagged. $T_{1/2}$ is calculated as $\ln(2) / \lambda_z$, where λ_z is the absolute value of the terminal elimination rate constant. A uniform weighting scheme in the regression analysis will be used to calculate the terminal elimination rate constant.

The following PK parameters will be calculated on Day -3 of PK-Lead-in of Cycle 1 in Dose Escalation:

- AUC_{inf} (Area under the plasma concentration-time curve from time of dosing extrapolated to infinity);
 $AUC_{\text{inf}} = AUC_{\text{last}} + C_{\text{last}} / \lambda_z$, where AUC_{last} is the area under the curve from 0 to the last quantifiable concentration, C_{last} is the last measurable plasma concentration and λ_z is the absolute value of the slope of the terminal log-linear phase.

The following PK parameters for only TAS3351 will be calculated on Day -3 of PK-Lead-in of Cycle 1 in Dose Escalation:

- CL/F (Apparent clearance);
CL/F will be calculated as $\text{Dose} / AUC_{\text{inf}}$;
- Vz/F (Apparent volume of distribution base on the terminal phase);
Vz/F will be calculated as $(\text{CL}/F) / \lambda_z$.

- MRT (Mean residence time);
MRT will be calculated as $AUMC_{inf}/AUC_{inf}$ where $AUMC_{inf}$ is the area under the first moment curve (AUMC) extrapolated to infinity

The following items will be calculated using PK parameters:

- RA (Accumulation ratio)
Individual RA of each PK parameter will be calculated as $RA(C_{max}) = C_{max} \text{ on Day 15} / C_{max} \text{ on Day -3}$, $RA(AUC_n) = AUC_n \text{ on Day 15} / AUC_n \text{ on Day -3}$, and $RA(AUC_{last}) = AUC_{last} \text{ on Day 15} / AUC_{last} \text{ on Day -3}$.
 $RA(AUC_{last})$ will not be calculated if the last sample was collected at different nominal timepoint between Day -3 and Day 15.

The following PK parameter will be calculated:

- MR (Metabolic ratio)
Individual MR of each PK parameters will be calculated as $MR(C_{max}) = C_{max} \text{ of TAS-05-14317} / C_{max} \text{ of TAS3351}$, $MR(AUC_n) = AUC_n \text{ of TAS-05-14317} / AUC_n \text{ of TAS3351}$, $MR(AUC_{last}) = AUC_{last} \text{ of TAS-05-14317} / AUC_{last} \text{ of TAS3351}$, $MR(AUC_{inf}) = AUC_{inf} \text{ of TAS-05-14317} / AUC_{inf} \text{ of TAS3351 on day -3 and Day 15}$. $MR(AUC_{inf})$ will be calculated only on Day -3.

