^c ECG must be collected prior to PK sampling. All ECGs through C3 should be performed in triplicate. Central ECGs will be performed for all timepoints unless otherwise specified.

^d This PK sample is mandatory for Dose Level 1. Following PK analysis for Dose Level 1, PK sampling at this timepoint at subsequent dose levels may be waived by the Sponsor, with this decision to be communicated to sites.

^e This PK sample must be collected prior to TAS3351 administration on this day. The ECG should be performed within 30 min prior to C1D1 dosing.

Table 14: Schedule for PK and ECG Sampling (BID Dosing)

Phase 1 Dose Escalation (Part A1)			
Day of Study^a	Collection time relative to TAS3351 administration (time window^b)	PK sample	ECG^c
Cycle 1 Day 1	Pre-dose (up to -30 minutes)		X
	0.5 hours (±10 minutes)	X	
	1 hour (±10 minutes)	X	X
	2 hours (±15 minutes)	X	X
	3 hours (±20 minutes)	X	
	4 hours (±25 minutes)	X	X
	6 hours (±35 minutes ^d)	X	
	8 hours (±45 minutes ^e)	X	X
	24 hours (±2 hours ^f)	X	
Cycle 1 Day 15	Pre-dose (up to -30 minutes)	X	X
	0.5 hours (±10 minutes)	X	
	1 hour (±10 minutes)	X	X
	2 hours (±15 minutes)	X	X
	3 hours (±20 minutes)	X	

Phase 1 Dose Escalation (Part A1)			
	4 hours (± 25 minutes)	X	X
	6 hours (± 35 minutes ^d)	X	
	8 hours (± 45 minutes ^e)	X	X
	24 hours (± 2 hours ^f)	X	
Cycle 2 Day 1	Pre-dose (up to -30 minutes)	X	X (Local)
Cycle 3 Day 1	Pre-dose (up to -30 minutes)	X	X (Local)

^a For patients with TAS3351 dose interruptions, PK days might be postponed or waived upon discussion and written approval by the Sponsor. Additional optional PK samples may be collected if any safety concerns are identified. If no longer needed for PK evaluation, collection time points might be skipped upon written notification by the Sponsor.

^b Time window given for guidance; collection outside these windows will not be considered a protocol deviation as long as the exact time of dosing and sampling is documented.

^c ECG must be collected prior to PK sampling. All ECGs through C3 should be performed in triplicate. Central ECGs will be performed for all timepoints unless otherwise specified.

^d Following PK analysis for Dose Level 1 (QD dosing), PK sampling at this timepoint may be waived by the Sponsor, with this communication to be communicated to sites.

^e This PK sample must be collected prior to administration of the second BID dose.

^f This PK sample must be collected prior to administration of the first BID dose on next study day.

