5.7.2.3. PK Parameter Summarization

The plasma PK parameters, C_{max} , AUC_n , AUC_{last} , AUC_{inf} , $T_{1/2}$, CL/F , Vz/F , MRT, $RA(C_{max})$, $RA(AUC_n)$, $RA(AUC_{last})$, $MR(C_{max})$, $MR(AUC_n)$, $MR(AUC_{last})$, $MR(AUC_{inf})$ and others as applicable will be listed by patient and summarized by dose level and treatment period, including number of observations (n), arithmetic mean, SD, CV%, minimum, median, maximum, geometric mean, geometric CV%. T_{max} will be listed by patient and summarized by dose level, and treatment period, including number of observations (n), minimum, median, and maximum.

The arithmetic mean, median, minimum, maximum, and geometric mean will be presented to the same decimal places as the individual values. SD will be presented to the same decimal place as

the mean. CV% and geometric CV% will be presented to 1 decimal place. PK parameters of secondary interest (R-square, R-square adjusted, the number of data points used for estimating λ_z , the upper and lower time point used for estimation of λ_z , λ_z itself, and $AUC_{\text{extrap}}\%$ will be listed by patient to enable verification of the exclusions, if any, of data from the summary statistics of the PK parameters of primary interest.

If a patient is treated with dose-modification or dose-interruption, concentrations from this patient on next PK collection date onward may be flagged and excluded from the summary statistics if deemed as appropriate.

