5.7.2.4. Dose-proportionality

Dose-proportionality of TAS3351 and TAS-05-14317 PK parameters on Day -3 and Day 15 will be evaluated based on both power regression analysis and one-way analysis of variance (ANOVA). Dose-proportionality will be assessed in C_{max} , AUC_{last} , AUC_n , AUC_{inf} on Day -3, and C_{max} , AUC_{last} , AUC_n on Day 15.

Regression analysis using power model

The power regression analysis will be performed using the following model:

$$\log(\text{AUCs or } C_{\text{max}}) = \alpha + \beta \times \log(\text{dose})$$

This model will be used to investigate the null hypothesis ($H_0: \beta=1$) with calculating 90% confidence intervals (CIs) for the power constant (β) with insignificance ($p < 0.05$) of testing the lack of fit. For a given parameter, a minimum of 3 values per dose level must be available for that dose level to be included in the power model.

One-way ANOVA

Prior to the analysis, dose-dependent parameters (C_{max} and AUCs) will be normalized with dose. All dose-normalized PK parameters will be log-transformed prior to the analysis, and then the differences in the means of dose levels will be tested by one-way ANOVA.

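### If BID dosing is explored, two rules in SAP 5.7.2.1 do not work as written: AUClast bridges an unsampled second dose, and the accumulation ratio divides by a Day -3 profile that BID patients do not have

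*SAP*

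**What the plan says.** BID dosing is a contingency. Protocol 6.1.1 allows it if PK, pharmacodynamic or safety data point that way, naming a short half-life or saturation of exposure as examples, and splits the daily dose into two equal doses about 12 hours apart.

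Protocol Table 14 (section 8.1) sets the BID sampling: profiles on Cycle 1 Day 1 and Day 15, at 0.5, 1, 2, 3, 4, 6, 8 and 24 h, plus a pre-dose sample on Day 15. The footnote to the 8 h sample reads "This PK sample must be collected prior to administration of the second BID dose". The 24 h sample is drawn before the next morning's dose. There is no Day -3 row.

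SAP 5.7.2.1 calculates parameters on Day -3 of "PK Lead-in (for QD dosing) or Day 1 (for BID dosing, if applicable) and Day 15". It then sets these rules:
- AUClast is the "Area under the curve from the time of dosing to the time of last quantifiable concentration", with no BID exception.
- AUCn "will be calculated by the program as a partial area depending on the dosing interval".
- Before AUCs are calculated, profiles are "evaluated on an individual basis as to their suitability for inclusion in these calculations". No BID criterion is attached.
- RA for Cmax, AUCn and AUClast is in each case Day 15 divided by Day -3. RA(AUClast) "will not be calculated if the last sample was collected at different nominal timepoint between Day -3 and Day 15".

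SAP 5.7.2.3 summarises AUClast and all three ratios. Under SAP 5.7.2.4, "PK parameters on Day -3 and Day 15 will be evaluated based on both power regression analysis and one-way analysis of variance", and AUClast is on the Day 15 list.

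**The concern.** The SAP adapts AUCn to the regimen but leaves AUClast and RA in their QD form.

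For AUClast, the last two BID samples sit on either side of the second dose. The trapezoid between them declines smoothly where the true curve rises to a second peak and falls again. This affects every BID profile, not an occasional one.

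For RA, the formula names a day with no BID profile. Read literally, the ratio has no denominator. Read sensibly, with Day 1 in its place, RA(AUClast) inherits the AUClast error from both days. The rule that withholds RA(AUClast) would not stop it. Under QD the last nominal samples differ (72 h on Day -3, 24 h on Day 15), so the rule applies. Under BID both days end at 24 h, so it does not.

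At stake are secondary PK results of Part A: the BID AUClast summaries, the Day 15 dose-proportionality entry for AUClast, and the BID accumulation ratios.

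**Working it through.** The plan states no figure on this point, so there is none to reproduce.

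**Inputs from the documents.** Doses at 0 and 12 h (Protocol 6.1.1). Sample times from Table 14. Linear-log trapezoidal rule (SAP 5.7.2.1), taken as linear while concentrations rise and logarithmic while they fall. 14 earlier days of BID dosing before Day 15, that is 28 earlier doses.

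**Inputs assumed.** Protocol 2.1.2.2 says there is no clinical experience, so half-life and absorption rate are assumptions: one-compartment oral model, linear PK, ka 0.5, 1 and 2/h, half-life 3, 6, 9 and 12 h (12 cases), with 24 and 48 h as a sensitivity range.

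**Formulas** (unit dose, unit volume). With ke = ln 2 / half-life, one dose gives C(t) = ka/(ka - ke) x (exp(-ke t) - exp(-ka t)). A profile is the sum over all doses given so far. A falling log segment has area (C1 - C2) x dt / ln(C1/C2).

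**One case in full: ka 1/h, half-life 6 h (ke 0.1155/h).**
- Day 15: C(8 h) = 0.5979, C(24 h) = 0.3769. Area 0-8 h by trapezoids = 6.69. Bridging segment = (0.5979 - 0.3769) x 16 / ln(0.5979/0.3769) = 7.66. AUClast = 6.69 + 7.66 = 14.35. True 0-24 h area at steady state = 2/ke = 17.31. Error = 14.35/17.31 - 1 = -17.1%.
- Day 1: C(8 h) = 0.4483, C(24 h) = 0.3533. AUClast = 4.723 + 6.383 = 11.106. True 0-24 h area = 14.254. Error = -22.1%.
- RA(AUClast) read as Day 15 / Day 1 = 14.354/11.106 = 1.292. The true 0-24 h ratio = 17.312/14.254 = 1.215, so the estimate is 6.4% too high.
- If a reviewer drops the 24 h sample, AUClast becomes the 0-8 h area: 6.69/17.31 = 39% of daily exposure.

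**Over the grid:**

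| Quantity (BID unless stated) | Half-life 3-12 h | Half-life 24-48 h |
|---|---|---|
| Day 15 AUClast against true 0-24 h | 6.5% to 33.5% low | 1.6% to 5.1% low |
| Day 1 AUClast against true 0-24 h | 13% to 35% low | 9% to 15% low |
| RA(AUClast), Day 15 / Day 1 | 2.5% to 10.0% high | 7.9% to 11.4% high |
| Day 15 area to 8 h only | 35% to 44% of daily exposure | not given |
| QD Day 15 AUClast, for comparison | 0.3% to 1.9% low | not given |
| AUCn (0-12 h) as now calculated, Day 15 | 2.0% to 4.8% high | not given |
| AUCn (0-12 h) as now calculated, Day 1 | 2.9% to 5.0% high | not given |
| RA(AUCn), Day 15 / Day 1 | 0.983 to 1.000 of true | not given |

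AUCn here takes the 12 h value by interpolation between 8 h and 24 h. It is slightly high, but by similar amounts on both days, so the ratio is nearly unbiased.

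**The case against.** The strongest reply is that the exposure measure that matters is already right. AUCn follows the dosing interval, is summarised, and is in the dose-proportionality analysis on both days. That stands, and it is why the remedy relies on AUCn. It does not repair AUClast, which is still reported for BID patients.

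Second, the SAP never calls AUClast daily exposure. True. But its definition ends at the last quantifiable sample, nominally 24 h, so true 0-24 h exposure is the right comparison for the interval it claims to cover.

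Third, profiles are reviewed individually. The review has no BID criterion, and its obvious action, removing the 24 h sample, turns AUClast into a 0-8 h area.

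Fourth, the RA denominator is easily inferred. Protocol 8.3.1 pairs the lead-in with QD and Cycle 1 Day 1 with BID before listing the accumulation ratio. This largely stands: for RA(Cmax) and RA(AUCn) the defect is an uncarried label. A reader may note that Protocol 4.2.1 and 6.1 describe a Day -3 dose for Part A1 without excluding BID. Even so, Table 14 schedules no BID samples that day.

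Fifth, the size depends on assumptions. At 24-48 h the Day 15 error is small, and saturation of exposure, the other named reason for BID, would break the linear model.

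A reader might also infer a biased dose-proportionality slope or a biased half-life. Neither is supported. Under linear PK the AUClast error is the same fraction at every BID dose, so a slope fitted to BID cohorts alone is unaffected. For half-life, the SAP leaves the choice of terminal points to visual inspection and adjusted R-squared, so it does not fix whether the 24 h sample enters the fit.

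**Conclusion.** The point holds for BID dosing only. AUClast is not a valid 0-24 h exposure under Table 14. RA as written names a profile that BID patients lack, and substituting Day 1 is sound for Cmax and AUCn but not for AUClast. The direction of the Day 15 AUClast error follows from the missing second peak. Its size, 6.5-33.5% at half-lives of 3-12 h and 1.6-5.1% at 24-48 h, rests on the assumed one-compartment linear model. The shorter range is relevant because a short half-life is one of the protocol's own reasons for going to BID.

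It would be too much to conclude that dose escalation or the RP2D is compromised. Escalation follows DLT counts, BID may never be used, and AUCn gives a usable BID exposure. This is a worthwhile clarification of low severity.

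**What to change.** Change the SAP only, before any BID cohort is analysed:

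1. In 5.7.2.1, state that for BID no AUClast is calculated across the second dose. Leave AUClast and RA(AUClast) out of the BID summaries (5.7.2.3) and BID dose-proportionality (5.7.2.4), and use AUCn (0-12 h) there.
2. Define BID RA(Cmax) and RA(AUCn) as Day 15 / Day 1.
3. The SAP does not say whether QD and BID cohorts share one power model. If they do, pair BID AUCn with the single dose, because Table 5 dose levels are total daily doses and AUCn covers only one of the two.
4. Optionally, let the Day 15 pre-dose value stand for 12 h when summarising Day 15 AUCn (error -1.4% to -0.3% at half-lives of 3-12 h). Keep the same 12 h method on both days for RA. Mixing the two would put RA(AUCn) between 0.986/1.050 = 0.94 and 0.997/1.029 = 0.97 of true, losing accuracy that it now has.

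A special rule extrapolating Day 1 from 8 to 12 h is not needed. RA(AUCn) is already within about 2% of true at half-lives of 3-12 h, and in 3 of the 12 modelled cases too few samples follow the peak by 8 h to extrapolate.

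The cost is a few lines of text, with no new sample or procedure. What is given up is a BID AUClast figure that could not be interpreted.

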5.7.2.2. Criteria to Estimate Elimination Parameters

The following acceptance criteria will be applied to elimination parameters ($T_{1/2}$, AUC_{inf} , CL/F , and Vz/F) to evaluate their reliability based on calculation of λz ;

- Sufficient number of time points (≥ 3) excluding C_{max} is available for calculating λz ;
- Adjusted RSQ is ≥ 0.75 ;
- $AUC_{extrap} \%$ (percentage of AUC_{inf} due to extrapolation from T_{last} [time of last quantifiable concentration] to infinity) is $\leq 30\%$.

If any of the criteria are not met for $T_{1/2}$, AUC_{inf} , CL/F , and Vz/F , they will be flagged in listings and excluded from summary statistics and statistical analyses.

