6.1.1. Dose Escalation

The starting dose of TAS3351 will be 50 mg QD (Table 5). The study is designed to escalate TAS3351 up to a dose of 700 mg daily based on safety and tolerability observed, with lower increments considered, if clinically relevant toxicities are observed. The upper end of 700 mg TAS3351 total daily dose levels are based on more conservative assumptions for PK predictions and non-clinical efficacy data observed. In case of toxicity, other dose levels, such as intermediate or dose levels lower than Dose Level 1, may be explored following discussion and agreement between the Sponsor and the Investigators.

Table 5: TAS3351 Dose Levels

Dose Level	Total Daily Dose (mg/d)	Absolute and % Change from Previous Total Daily Dose
-1	25	-25 mg / -50%
1 (Starting dose)	50	-
2	100	50 mg / 100%
3	200	100 mg / 100%
4	350	150 mg / 75%
5	500	150 mg / 43%
6	700	200 mg / 40%

Note: If no DLTs observed at 700 mg QD, any further dose escalation will not exceed 33% increments.

In addition, if PK, pharmacodynamic, and/or safety data indicate that splitting the dose of TAS3351 in two daily doses might be preferable (eg, due to short half-life, saturation of exposure), then twice daily (BID) dosing of TAS3351 may be explored following discussion and agreement between the Investigators and the Sponsor. In such case, the dose of the highest QD dose shown previously to be safe and tolerable will be divided into two equal doses to be taken in the morning and evening approximately 12 hours apart. Dose escalation for twice daily dosing will follow total daily doses shown in Table 5 (ie, total daily dose divided by 2 for BID dosing).

The planned dose escalation will follow a BOIN design, [REDACTED]. For further information about statistical considerations, please see Section 12.

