8. PHARMACOKINETICS

8.1. Sample Collection

Blood samples for PK analysis and ECG sampling will be collected at specific time points listed in Table 13 (Table 14 in case BID dosing will be explored) and used to evaluate PK of TAS3351 and its active metabolite (TAS-05-14317). ECGs should also be obtained prior to on-site TAS3351 administration. When a 12-lead ECG is obtained at the same timepoint as a PK blood draw, the 12-lead ECG should be obtained first.

Detailed information about collection procedures including blood sampling, collection, processing, and sample shipment will be provided in a separate Laboratory Manual.

Table 13: Schedule for PK and ECG Sampling (QD Dosing)

Phase 1 Dose Escalation (Part A1)			
Day of Study ^a	Collection time relative to TAS3351 administration (time window ^b)	PK sample	ECG ^c
PK Lead-in, Day -3	Pre-dose (up to -30 minutes)		X
	0.5 hours (±10 minutes)	X	
	1 hour (±10 minutes)	X	X
	2 hours (±15 minutes)	X	X
	3 hours (±20 minutes)	X	
	4 hours (±25 minutes)	X	X
	6 hours (±35 minutes)	X	
	8 hours (±45 minutes ^d)	X	X
	24 hours (±2 hours)	X	X
	48 hours (±2 hours)	X	
	72 hours (± 2 hours ^e)	X	X
Cycle 1 Day 15	Pre-dose (up to -30 minutes)	X	X
	0.5 hours (±10 minutes)	X	
	1 hour (±10 minutes)	X	X
	2 hours (±15 minutes)	X	X
	3 hours (±20 minutes)	X	
	4 hours (±25 minutes)	X	X
	6 hours (±35 minutes)	X	
	8 hours (±45 minutes ^d)	X	X
	24 hours (±2 hours ^e)	X	X
Cycle 2 Day 1	Pre-dose (up to -30 minutes)	X	X (Local)
Cycle 3 Day 1	Pre-dose (up to -30 minutes)	X	X (Local)

Phase 1 “Backfill” (Part A2), Dose Expansion (Part B), and Phase 2 (Part C)			
Day of Study^a	Collection time relative to TAS3351 administration (time window^b)	PK sample	ECG^c
Cycle 1 Day 1	Pre-dose (up to -30 minutes)	X	X (Local)
	2 hours (±1 hour)	X	X (Local)
Cycle 2 Day 1	Pre-dose (up to -30 minutes)	X	X (Local)
	2 hours (±1 hour)	X	X (Local)
Cycle 3 Day 1	Pre-dose (up to -30 minutes)	X	X (Local)

^a For patients with TAS3351 dose interruptions, PK days might be postponed or waived upon discussion and written approval by the Sponsor. Additional optional PK samples may be collected if any safety concerns are identified. If no longer needed for PK evaluation, collection time points might be skipped upon written notification by the Sponsor.

^b Time window given for guidance; collection outside these windows will not be considered a protocol deviation as long as the exact time of dosing and sampling is documented.

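### SAP 5.7.2.2 screens T1/2 on AUC extrapolation, which T1/2 does not use, so longer half-lives drop out of its summaries; MRT and MR(AUCinf), which do use it, are not screened

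*SAP*

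**What the plan says.** SAP 5.7.2.2 opens: "The following acceptance criteria will be applied to elimination parameters", and names four: T1/2, AUCinf, CL/F and Vz/F. The criteria are at least three points for λz excluding Cmax, adjusted RSQ of at least 0.75, and AUCextrap% of at most 30%. When any one fails, "they will be flagged in listings and excluded from summary statistics and statistical analyses". The section does not limit the criteria to a study day.

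SAP 5.7.2.1 plans T1/2 for both full-profile days: Day -3 (or Cycle 1 Day 1 under BID dosing) and Cycle 1 Day 15. It derives T1/2 as ln(2)/λz. AUCinf is restricted to the lead-in: "The following PK parameters will be calculated on Day -3 of PK-Lead-in of Cycle 1 in Dose Escalation". Protocol 8.3.1 has the same restriction. MRT is AUMCinf/AUCinf, for TAS3351 on Day -3. MR(AUCinf) is the metabolite-to-parent ratio of AUCinf, also on Day -3 only.

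SAP 5.7.2.3 summarises MRT and MR(AUCinf) together with T1/2, and gives neither an exclusion rule of its own. Under QD dosing, Protocol Table 13 ends sampling at 72 h after the Day -3 dose and at 24 h on Day 15.

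**The concern.** AUCextrap% is fixed largely by two things: the length of sampling and the half-life. Using it to decide which half-lives enter a summary is selection on the quantity being summarised. Short values pass, long values fail, and the summary moves down.

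The screen also covers the wrong parameters. T1/2 needs only the λz fit, yet it is tested. MRT needs AUCinf, and its numerator depends even more on the extrapolated tail, yet it is not tested. The SAP could therefore reject a patient's AUCinf and still summarise an MRT and an MR(AUCinf) computed from it.

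T1/2 is a named secondary PK endpoint for Part A (Protocol 3.1; SAP Table 1), and the protocol synopsis gives assessment of terminal elimination as the purpose of the lead-in. If Day 15 were screened too, the lower cut-off there could make half-life look shorter at steady state than after the first dose through truncation alone.

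**Working it through.** **Inputs from the documents.** 30% limit (SAP 5.7.2.2); T1/2 = ln(2)/λz and MRT = AUMCinf/AUCinf (SAP 5.7.2.1); last QD sample at 72 h ± 2 h on Day -3 and 24 h ± 2 h on Day 15 (Protocol Table 13). The documents state no half-life cut-off, so there is no figure of theirs to reproduce.

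**Step 1: the cut-off implied by 30%.** For a mono-exponential decline the extrapolated share of AUCinf is exp(−λz × Tlast). At steady state the same expression holds with Tlast equal to the dosing interval. Setting it to 0.30:

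T1/2 = ln(2) × Tlast / ln(1/0.30) = 0.693 / 1.204 × Tlast = 0.576 × Tlast

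- Day -3: 0.576 × 72 = 41.4 h (40.3 to 42.6 h for a last sample at 70 to 74 h).
- Day 15, if screened: 0.576 × 24 = 13.8 h (12.7 to 15.0 h for a last sample at 22 to 26 h).

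The limit is the same as requiring 1.204 / 0.693 = 1.74 half-lives of sampling.

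**Step 2: dependence on the model (shape parameters assumed).**

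| Profile | Day -3 cut-off | Day 15 cut-off |
|---|---|---|
| First-order absorption, ka 0.3 to 5 per h | 39.5 to 41.3 h | 12.3 to 13.7 h |
| Linear-log trapezoid on Table 13 times, ka 0.5 to 2 per h | 40.2 to 41.1 h | 12.6 to 13.6 h |
| Bi-exponential, 90% of AUC in terminal phase | 45.4 h | 15.1 h |
| Bi-exponential, 70% | 58.9 h | 19.6 h |
| Bi-exponential, 50% | 97.7 h | 32.6 h |

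Every model excludes the longer half-lives; only the cut-off moves.

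**Step 3: effect on summarised T1/2.** Human half-life is not given, so a range is used. Assume log-normal T1/2 with 40% CV, so σ = √ln(1 + 0.4²) = 0.385, and the mono-exponential cut-offs. With z = ln(cut-off / GM) / σ, the share kept is Φ(z) and the geometric mean of those kept is GM × exp(−σ × φ(z) / Φ(z)). Example, GM 16 h on Day 15: z = ln(13.8/16)/0.385 = −0.38, Φ = 0.35, φ = 0.37, giving 10.7 h.

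| True geometric mean | Day -3: kept; summarised | Day 15, if screened: kept; summarised |
|---|---|---|
| 8 h | 100%; 8.0 h | 92%; 7.5 h |
| 12 h | 99.9%; 12.0 h | 64%; 9.6 h |
| 16 h | 99.3%; 15.9 h | 35%; 10.7 h |
| 20 h | 97.1%; 19.5 h | 17%; 11.3 h |
| 40 h | 54%; 30 h | under 1%; no useful summary |

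**Step 4: MRT.** For a mono-exponential decline the extrapolated share of AUMCinf is exp(−x) × (1 + x), with x = λz × Tlast. At the 30% limit x = 1.204, so the share is 0.30 × 2.204 = 0.66. When 30% of AUCinf is extrapolated, about 66% of AUMCinf is.

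**Step 5: Day 15.** AUCextrap% is a percentage of AUCinf. SAP 5.7.2.1 and Protocol 8.3.1 plan AUCinf only for Day -3, while T1/2 is planned on both days and the criteria name no day. A programmer must either derive an unplanned Day 15 AUCinf or leave the criterion out, and the two choices give different T1/2 tables.

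**The case against.** The other side has a good case on several points.

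- **The rule has a purpose.** The SAP presents it as a reliability check on λz, and requiring about 1.74 half-lives of sampling is a crude span check. That stands as a reason to check span, but not as a reason to leave the long values out of the summary.
- **Day -3 is the day designed for half-life, and bias there is small over most of the range.** This stands up to a true geometric mean of about 20 h. Nothing in the documents shows that a value near 40 h is likely.
- **Nothing is lost from the record.** Failing values stay flagged in the listings, and SAP 5.7.2.3 also lists λz, its time points, adjusted R-square and AUCextrap% by patient. This stands: the exclusion affects summaries and analyses, and it can be traced and reversed.
- **MRT is not a named endpoint.** True, and no decision in the documents uses it. The inconsistency remains.

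A reader might also infer two stronger claims. The first is that half-lives above 14 h will certainly be excluded on Day 15. The documents do not establish this, because the denominator is not planned for that day. The second is that the rule would distort the choice of BID dosing, since Protocol 6.1.1 gives as one possible reason that "splitting the dose of TAS3351 in two daily doses might be preferable (eg, due to short half-life, saturation of exposure". That choice follows discussion between investigators and the sponsor and may draw on PK, pharmacodynamic or safety data. The SAP governs tables for the CSR, with primary analyses after safety follow-up or six months from last enrolment. No passage ties the BID decision to these screened summaries.

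**Conclusion.** The point holds as a defect in how the criterion is scoped. AUCextrap% is applied to a parameter that does not depend on AUCinf and is not applied to two that do. As written, it truncates summarised T1/2 from above and leaves the Day 15 rule undefined.

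The size depends on a human half-life that the documents do not give. Under a mono-exponential decline and an assumed 40% CV, Day -3 bias is negligible up to a true geometric mean of about 20 h (19.5 h summarised) and material near 40 h (30 h summarised). If the screen is run on Day 15, bias is small at 8 h and material from about 12 h (9.6 h summarised). A distribution phase raises the cut-offs and slow absorption lowers them slightly; the direction does not change. The cut-offs are for QD dosing.

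**What to change.** In SAP 5.7.2.2:

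1. Apply AUCextrap% of at most 30% only to Day -3 AUCinf, CL/F, Vz/F, MRT and MR(AUCinf).
2. Accept T1/2 on Day -3 and Day 15 on number of points and adjusted RSQ. Flag, but do not exclude, values whose fitted span is under about 2 half-lives.
3. State that AUCextrap% is not applied on Day 15.

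An effective half-life from the accumulation ratio is not recommended as a Day 15 substitute. It is undefined when the ratio is 1 or less, which happens mainly with short half-lives. It also assumes time-invariant kinetics, although Protocol 2.1.2.1.2 reports time-dependent CYP3A inhibition in vitro.

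The cost is SAP wording and one flag in the listings, with no new samples. The downside is that some retained T1/2 values are less precise. On Day 15 the fitted span cannot exceed the nominal 24 h, so any T1/2 above about 24/2 = 12 h will carry the flag. The flag, with the median already planned in SAP 5.7.2.3, handles this.
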